#### **Event Rates**

The number of people of events should be recorded in detail and showing the event rate in 90 days of each treatment group in summary statement.

The event rate for each treatment group will be calculated as: the sum of number of event for all the patients / the number of patients enrolled in this group.

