## (1) Adverse events

The number of cases and events of AE, adverse reactions, AE causing drop-out and SAE are calculated respectively, and a detailed list is provided. The incidence is calculated using the number of people in each safety dataset as the denominator, and the Chi-square test or Fisher's exact probability method is used for inter-group comparison when necessary.

The number of cases and events of the events mentioned in the above endpoints are counted according to the systematic organ classification and preferred terms encoded by MEDDRA, as detailed in the Statistical Analysis protocol (SAP).

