#### Safety Set (SS)

All patients who received at least 1-time of study drug according to the study protocol and safety assessment available will be included in the safety population. Throughout the safety results sections, erroneously treated patients (eg, those randomized to rhTNK-tPA group but actually given rhTNK-tPA) will be accounted for in the actual treatment group. This population will be used for safety analyses.

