#### 13. Safety Analyses

All analyses of safety data will be carried out using the safety set (SS) population.

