#### **Bleeding Events**

The incidence of symptomatic intracranial hemorrhage within 36 hours (as defined by ECASS III criteria);

The incidence of symptomatic intracranial hemorrhage within 90 days (as defined by ECASS III criteria);

The incidence of PH2 intracranial hemorrhage within 36 hours (according to SITS criteria);

The incidence of any intracranial hemorrhage within 90 days;

The incidence of other significant hemorrhage events within 90 days (as defined by GUSTO criteria).

For most bleeding events, the number of bleeding events occurring over the treatment period will be summarized and Chi-squared test or Fisher's Exact test will be used to compare the number of bleeding events between treatment groups. This will also be tested by logistic regression model. The odds ratio with 95% CI will be reported.

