#### **Adverse Events**

Adverse events (AEs) will be coded using the MedDRA coding dictionary (Version 6.0 or a later release) and grouped by system organ class (as detailed in the study protocol). Separate data display listings and summaries will be presented for adverse events that start prior to first dose of study medication (pre-treatment), whilst on study medication (during treatment) and after the last dose of study medication (post-treatment).

Within each treatment group, the number and percentage of patients experiencing an AE will be summarized by system organ class and preferred term and Chi-squared test or Fisher's Exact test will be used to compare the number of each grouped AE event between treatment groups. In addition, a separate summary will be provided for AEs experienced by more than 5% of patients in either of the treatment groups.

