#### **Deaths and Serious Adverse Events**

Summary tables and data displays will be provided for serious adverse events (as detailed in the study protocol). In addition, all deaths and serious AE's will be documented in a case narrative format in the clinical study report.

The number of deaths occurring over the treatment period will be summarized and Chi-squared test or Fisher's Exact test will be used to compare the number of deaths between treatment groups.

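### The final SAP's safety rules count events instead of patients, divide by patients enrolled instead of the Safety Set, and use an undefined treatment period

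*Supplement*

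**What the plan says.** The final SAP (version 1.3) and final protocol (V2.2) give these rules.

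- **SAP 10, Event Rates.** The first sentence concerns people and 90 days: "The number of people of events should be recorded in detail and showing the event rate in 90 days of each treatment group". The formula that follows concerns events: "the sum of number of event for all the patients / the number of patients enrolled in this group".
- **SAP 13, opening line.** "All analyses of safety data will be carried out using the safety set (SS) population".
- **SAP 7, Safety Set.** "All patients who received at least 1-time of study drug according to the study protocol and safety assessment available will be included". Wrongly treated patients are counted under the drug they actually received.
- **SAP 13, Bleeding Events.** After listing endpoints at 36 hours or 90 days, the SAP says "the number of bleeding events occurring over the treatment period will be summarized". The number of bleeding events is then compared by chi-square or Fisher, with logistic regression and an odds ratio added.
- **SAP 13, Adverse Events.** Patients with an event are summarised as numbers and percentages, but the chi-square or Fisher test is used to "compare the number of each grouped AE event between treatment groups".
- **SAP 13, Deaths.** "The number of deaths occurring over the treatment period will be summarized". The endpoint in SAP 3 is 90-day mortality.
- **Protocol 12.5, Adverse events.** "The incidence is calculated using the number of people in each safety dataset as the denominator".

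**The concern.** Three elements of a safety rate are in conflict: what is counted, over whom, and over what time.

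Chi-square and Fisher tests on a 2x2 table assume one independent yes/no per patient. If a patient with three nosebleeds adds three to the count, the counts vary more than the test allows and the p-value is too small. A sum of events over patients is a mean number of events, not an incidence, and it can pass 100%.

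Enrolled patients, as randomised, are a different group from dosed and assessed patients by drug received.

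A treatment period has no obvious meaning when the drug is given once and outcomes are followed for 36 hours or 90 days.

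The bleeding, adverse event and mortality comparisons are the safety half of the trial's conclusion. The trial is open label, so these choices should not be left until programming.

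**Working it through.** **1. The plan's own figure.** The documents give no event-rate figure for this trial. The enrolled denominator is 715 per arm (SAP 6), which reproduces closely. With control rate 0.5932, test rate 1.07 x 0.5932 = 0.6347, threshold 0.937, one-sided alpha 0.025 and power 0.85, the log-RR formula is

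n = (1.960 + 1.036)² x [(1 - 0.6347)/0.6347 + (1 - 0.5932)/0.5932] / [ln(1.07/0.937)]² = 642.8.

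The Farrington-Manning score formula gives 642.0, against 642 stated. Dropout: 642/0.9 = 713.3, rounded up to 714, against 715 stated. Sample size is not affected by this point.

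**2. Denominator.** Rate on enrolled = rate on Safety Set x (Safety Set size / 715). The Safety Set size is an assumption.

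| Safety Set per arm | A true 3.0% becomes | Relative understatement |
|---|---|---|
| 700 | 2.94% | 1 - 700/715 = 2.1% |
| 680 | 2.85% | 4.9% |
| 643 | 2.70% | 10.1% |

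The last row treats the planned 10% dropout as lost from the Safety Set. That is pessimistic, since a patient who is dosed and assessed once stays in.

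**3. Unit of count.** Let p be the share of patients affected and m the mean events per affected patient, with events per affected patient = 1 + Poisson(m - 1). The true variance per patient is p[(m - 1) + m²] - (pm)². The chi-square on events assumes pm(1 - pm). With both arms alike, the test rejects with probability about 2[1 - Φ(1.96/√ratio)].

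Example with p = 0.10, m = 1.5: true variance 0.10 x 2.75 - 0.0225 = 0.2525; assumed 0.15 x 0.85 = 0.1275; ratio 1.98; rejection about 16%. Simulation (20,000 null trials, 715 per arm, two-sided 5%) agrees:

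| p | m | Test on patients | Test on events |
|---|---|---|---|
| 0.02 | 1.0 | 4.8% | 4.8% |
| 0.05 | 1.1 | 4.9% | 7.3% |
| 0.10 | 1.2 | 4.9% | 10.3% |
| 0.10 | 1.5 | 4.9% | 16.5% |
| 0.20 | 1.5 | 5.2% | 18.8% |
| 0.20 | 2.0 | 5.2% | 29.2% |

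A second model with negative-binomial counts (shape 0.5 or 1) gives about 6-7% at 0.02-0.05 events per patient, 8-9% at 0.10, 11-14% at 0.20 and 15-33% at 0.3-0.5. Above one event per patient, no 2x2 table can be formed. The documents give no events per patient, so p, m and the dispersion are all assumptions.

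**4. Can the formula exceed 100%?** In the protocol's phase 2 table of common adverse events (section 1.2), the 52 preferred-term rows sum to 121 in 57 patients at 0.25 mg/kg and 160 in 59 on rt-PA: 121/57 = 212% and 160/59 = 271%. These sums pool all terms, so they bear on an overall adverse event rate. They do not bear on the term-by-term tests: the largest single row is 12/57 (21%) in the first arm and 11/59 (19%) in the second.

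**5. Window.** SAP 3 and the endpoint list in SAP 13 give 36 hours or 90 days. The test sentences for bleeds and deaths give the treatment period, with no definition.

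**The case against.** **Patient-level analysis is also specified.** The sentence before the formula speaks of people. The adverse event summary is in patients. Logistic regression for bleeding needs one yes/no per patient. The Safety Set is named for all safety analyses, and protocol 12.5 compares incidences. A sensible programmer could reach the right tables. This stands as evidence of intent, but it does not settle the rule. The added regression covers bleeding only, so the adverse event test is untouched. Nor does deferring to the other document help: SAP 9 sends the reader to the protocol for detail, while protocol 12.2 and 12.5 send the reader to the SAP.

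**The main safety endpoints barely move.** This stands. A patient dies once, so event and patient counts agree. Symptomatic hemorrhage and PH2 rarely recur in one patient. For single preferred terms, phase 2 frequencies point to the lower rows of the inflation figures.

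**A reader might infer that the treatment period means the dosing time,** 5-10 seconds in one arm and up to an hour in the other, because SAP 13 separates adverse events on medication from those after the last dose. The safety tables would then be nearly empty and unequal by arm: at an assumed 5% 90-day mortality with constant hazard, 715 x 0.05/2160 = 0.017 deaths per arm in an hour, against about 36 over 90 days. The documents do not support this reading. The SAP never defines the term that way, Event Rates refers to 90 days, and the bleeding section lists each window just before the test. SAP 11 uses the term for prohibited concurrent medication, which protocol 6.2 restricts for 24 hours after dosing. What remains is an undefined term that does not match the endpoints.

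**Conclusion.** Wrong as written. The rate formula, the test unit for adverse events and bleeds, and the counting window each conflict with the SAP's own endpoints, its Safety Set rule or the protocol. This is a conflict between stated rules, not merely missing detail.

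The size depends on the outcome:

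- **Deaths:** the unit of count has no effect. The denominator and window still need correcting.
- **Symptomatic intracranial hemorrhage and PH2:** the unit has little effect.
- **Recurrent adverse events, system-organ-class groupings and repeat bleeds:** type I error of about 7% at 1.1 events per affected patient and 17-19% at 1.5 (10-20% of patients affected).
- **All rates:** understated by 2-10% relative if the Safety Set is 700-643 of 715.

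A reader might conclude that the trial's safety incidences and p-values are wrong. That goes too far. They would be wrong only if the literal sentences were programmed over the patient-level rules that also appear, and the p-value error rests on event frequencies the documents do not give.

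**What to change.** Amend the SAP wording before unblinding:

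1. In section 10, define every safety rate as Safety Set patients with at least one event within the endpoint's window, divided by Safety Set patients, by treatment received.
2. In section 13, run the chi-square or Fisher test, the odds ratio and the risk difference on that patient-level outcome for bleeds, deaths and each adverse event grouping.
3. Report total event counts descriptively only, without a test.
4. Replace the treatment-period phrase for bleeds and deaths with 36 hours or 90 days, as each endpoint states.

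The cost is SAP text and the matching table shells. No new data are needed, and the result agrees with protocol 12.5.

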#### 11. Study Population

#### Disposition of Participants

The number of patients in each analysis population will be presented, patients to be excluded from the Per Protocol population will be listed, and the total number of patients attending each clinic visit will also be summarized by treatment group.

The number of patients randomized, completed and prematurely withdrawn from the study will be presented for each treatment group. The primary reasons for withdrawal both prior to and post randomization will also be presented.

A data display listing and summary of deviations from the inclusion/exclusion criteria will be presented for all patients who were either entered or randomized into the trial.

#### **Protocol Deviations**

Participant data will be examined for evidence of protocol violators in order to assess how well the protocol was followed. Inclusion and exclusion criteria are detailed in the study protocol.

Participants who commit protocol violations will be included in the FAS Population but

excluded from the Per Protocol Population. These protocol violations will be shown in a listing. Patients can either be full or partial protocol violators. A full protocol violator is completely excluded from the Per Protocol Population. A partial protocol violator has only some data excluded. For those who violated the protocol during the treatment period due to unpermitted changes in the medication or prohibited concurrent medication, the analysis will only use data recorded prior to the violation. For all violations which reference the treatment period, the treatment start date will be used as the reference date.

A listing of all possible protocol violators will be produced for clinical review. The final list of patients who are protocol violators and are therefore excluded from the Per-Protocol population will be agreed by the study team.

#### Demographic and Baseline Characteristics

Demographic, medical histories and baseline characteristics information will be listed and summarized for patients in each treatment group based on the FAS population.

The continuous data followed normal distribution will be presented as mean and standard deviation, and the continuous data followed skewness distribution will be presented as median and interquartile range; categorical data will be presented as n(%). T-test or Wilcoxon rank sum test will be used for comparison between two continuous data, and Chi-squared tests or Fisher exact test will be used for comparison between two categorical data.

#### 12. Efficacy Analyses

Primary efficacy analysis will be performed using FAS and PPS populations. The analyses for the primary efficacy endpoint will be conducted by one-sided test with a significance level of one-sided  $\alpha$ =0.025. All other statistical analyses will use a 2-sided test at the 5% level of significance.

#### Primary Efficacy Analysis

The primary endpoint is the proportion of patients with 90-day mRS score of 0-1.

#### Main Model

The proportion of patients with 90-day mRS score of 0-1 between treatment groups will be

compared by Cochran-Mantel-Haenszel Chi-squared tests with the adjustment of center effect. Effect rate with 95% CI in each treatment group and the RR or RD of effect rates between the two groups and corresponding 95% CI will be reported. This will also be tested by logistic regression model with the adjustment of center effect and mRS scores at baseline. The odds ratio with 95% CI will be reported. According to the protocol, superiority of the treatment group will be tested if the non-inferiority is met.

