### **Research Flow Chart**

Measures		Screening/B aseline	Treatment period			follow-up		
		4.5 h. (Before thrombolysi s)	0h (Thrombolytic Therapy)	24 h + 2 h	24h-36h	7±1 day or before discharge (whichever occurs first)	90±7 days/early end of visit	
	ing Informed Consent	X						
	emographic aracteristics	X						
Sympto	ms of this onset	X						
Med	dical history	X						
Prior	medication1	X						
	oncomitant ation/treatment 	X	X	X	X	X	X	
V	ital signs 	X	X	X		X		
	mRS	X 					X	
	NIHSS	X		X		X		
	BI scale						X	
EQ	- 5 D scale						X	
Blood/t	urine pregnancy	X						
	Routine blood test	X		X		X		
Labora	Blood biochemistry	X		X		X		
exami nation 	Coagulation function	X		X		X		
	Routine urinalysis			X		X		
	rocardiogram (ECG) 	X				X		
C	T or MRI 	X			X			
ran	domization	X						
	rombolysis formation 		X					
Advers	e Events/Serious dverse Events		X	X	X	X	X	

- 1. Prior medication is only recorded for drugs that fall into the restrictions in the inclusion/exclusion criteria.
- 2. The "blood pressure" of screening and enrollment is collected when vital signs are collected. "0h" is regarded as the monitoring results of vital signs within 5min before thrombolysis. Vital signs include blood pressure, pulse, body temperature and respiratory

rate

- 3. The mRS score at screening include pre-onset score and post-onset pre-thrombolysis score.
- 4. Blood/urine pregnancy test is applicable to fertile women only;
- 5. Laboratory examination:
  - 1) Baseline laboratory tests include routine blood test, blood biochemistry, and coagulation function; Subjects will not need to repeat the test if they have already performed some laboratory tests between the present onset and prior to thrombolysis. For baseline blood lipid tests (total cholesterol (TC), low density lipoprotein (LDL-C), high density lipoprotein (HDL-C), triglyceride (TG)), the most recent fasting blood lipid is collected after the onset of the disease. Blood glucose test is performed at baseline. Peripheral blood glucose is measured as one of the inclusion and exclusion criteria, and venous blood is collected for blood glucose test. Blood biochemical results are allowed to be obtained after the study drug has been administered. If abnormal blood biochemical results are obtained, they will be handled by the study physician in accordance with the discipline guidelines and the clinical management pathway of the hospital.

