#### 4. Study population

#### 4.1 Inclusion criteria

(1) Age  $\geq$ 18 years, male or female;

- (2) Time from onset to treatment < 4.5h; the time of symptom onset is defined as "the last time point at which the patient appears normal";
- (3) Clinical diagnosis as ischemic stroke (the diagnosis following the *Chinese Guidelines for the Diagnosis and Treatment of Acute Ischemic Stroke 2018*);
- (4) MRS score of 0-1 before onset;
- (5) 4 < NIHSS < 26 at baseline;
- (6) Subjects or their guardians voluntarily sign the informed consent.

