## 7. Study process

## 7.1 Screening/baseline assessment

- 1) Demographic information: sex, age, ethnicity.
- 10) The time of present onset as well as the symptoms (the present onset symptoms are mainly reflected in NIHSS score).
- 11) Risk factors (past medical history and history of present illness): high blood pressure, diabetes, cerebral infarction, TIA, coronary heart disease, myocardial infarction, arrhythmia, always oral medication (aspirin, clopidogrel, and warfarin, antihypertensive drugs, lipid-lowering drugs, oral glucose-lowering drugs, drug adjust heart rate), dementia, peripheral artery disease, lipid metabolic disorders, liver and kidney function is not complete, and neck intracranial vascular stenosis or deformity, smoking, drinking alcohol.
- 12) Prior and concomitant medication.
- 13) Vital signs (blood pressure, pulse, respiratory rate and body temperature).

- 14) MRS score before onset, MRS score post onset before onset of thrombolysis, NIHSS score post onset before onset of thrombolysis.
- 15) Electrocardiogram (If the subject has had an electrocardiogram before thrombolysis after the onset of the disease, no repeat examination is required).
- 16) Imaging (CT or MRI).

Screening/baseline imaging examination is "CT or MRI", which is used to exclude hemorrhagic stroke; the CT or MRI results generated by other hospitals can also be used as a screening basis, if the study physician deems them acceptable; if a subject has undergone a CT or MRI check post symptom onset before onset of thrombolysis, such examination may be omitted. CT or MRI evaluation should include: cerebral hemorrhage, acute severe symptomatic ischemia in the area of blood supply, or other pathological changes.

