### 12.4 Efficacy evaluation

Primary efficacy endpoints

Description method: Patients with 90-day MRS score of 0-1 among all enrolled patients in the corresponding data set is statistically described in the form of number and percentage respectively.

Analysis methods: in this protocol, the primary endpoint is the proportion of subjects with 90-day mRS score of 0-1; for such endpoint, CMH test with controlled

center effect will be applied to statistically compare the treatment group and control group, and the 95% confidence interval of efficacy, and corresponding RR or RD and corresponding 95% confidence interval will be calculated; Logistic regression model analysis will also be considered to report the 95% confidence intervals of OR for TNK-TPA versus rt-PA. Adjustment for covariates with inter-group differences or center-group interactions will be made as appropriate.

Analysis of secondary efficacy endpoints

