#### 4. Statistical Hypotheses

Comparison of the primary efficacy endpoint between groups is conducted by a one-sided test, with a significance level of one-sided  $\alpha$ =0.025. Null hypothesis H0: RR  $\leq \Delta$  and alternative hypothesis H1: RR  $> \Delta$ ; when P < 0.025, or lower limit of 95% CI of RR  $> \Delta$ , it indicates that the test drug is not inferior to control drug; RR is the ratio of incidence of the treatment group and the control group,  $\Delta$  is the non-inferior margin, 0.937 in this trial. All other statistical analyses are conducted by two-sided tests, with a significance level of two-sided  $\alpha$  =0.05. When P  $\leq$  0.05, it indicates a statistically significant difference. Non-inferiority hypothesis tests are as follows:

H0: 
$$RR$$
 Treatment group/control group  $\leq \Delta$   
H1:  $RR$  Treatment group/control group  $> \Delta$ 

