#### 6. Sample size estimates

In this study, rt-PA active control will be used based on a statistical hypothesis test of non-inferiority, and the proportion of patients with 90-day mRS score of 0-1 will be used as the primary efficacy endpoint.

According to a paper published in the Lancet [1] in 2014 about meta-analysis of the proportion of 90-day mRS score of 0-1 (treatment within 4.5h) regarding rt-PA versus Placebo, the RR and 95% confidence interval were 1.24 and 1.14-1.36, respectively. According to the *Guidelines for the Design of Non-inferiority Drug Clinical Trials* [2], the lower 95% confidence interval of the Meta analysis should be used to calculate the non-inferiority threshold given that the primary endpoint is a high priority index. Therefore, based on the lower CI limit of 1.14, together with an efficacy of 50% of the active control, the non-inferior threshold was determined as 0.937. Then assuming  $\alpha$ =0.025 using one-sided test, power 1- $\beta$ =0.85, treatment group (TNK) incidence of 63.64%, control group (rt-PA) incidence of 59.32%, RR= 1.07, the sample size was calculated to be 642 cases in each group; considering a dropout rate of 10%, the sample size was determined as 715 cases in each group and the total sample size is estimated to be 1430 cases.

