#### Secondary Efficacy Analyses

#### The proportion of patients with an mRS score of 0-2 at 90±7 days

The proportion of patients with 90-day mRS score of 0-2 in treatment groups will be compared by Chi-squared tests. This will also be tested by logistic regression model. The odds ratio with 95% CI will be reported.

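### No planned efficacy analysis adjusts for baseline NIHSS or age; the one patient-level covariate is undefined, and the protocol lets others be chosen from observed imbalance

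*Supplement*

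**What the plan says.** **Decision rule.** SAP section 4: "Comparison of the primary efficacy endpoint between groups is conducted by a one-sided test", at one-sided 0.025, on the risk ratio (RR). SAP section 6: "the non-inferior threshold was determined as 0.937".

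**Primary analysis.** SAP section 12, Main Model, has a CMH comparison adjusted for centre, with RR or RD and 95% CI. It adds a "logistic regression model with the adjustment of center effect and mRS scores at baseline", reported as an odds ratio.

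**Which mRS.** Flow chart note 3 of the final protocol: "The mRS score at screening include pre-onset score and post-onset pre-thrombolysis score". Inclusion criterion 4 requires "MRS score of 0-1 before onset". Neither document says which score the model uses.

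**Secondary endpoints.** For mRS 0-2 the groups "will be compared by Chi-squared tests. This will also be tested by logistic regression model". No covariates are named there, nor for the ordinal mRS, NIHSS-response and Barthel models. EQ-5D is compared by t-test or rank sum test. SAP section 9 (Multicenter Studies) requires the centre effect to be dealt with but gives no method.

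**Open rule.** Protocol 12.4: "Adjustment for covariates with inter-group differences or center-group interactions will be made as appropriate". Protocol 12.2 likewise leaves baseline or centre adjustment to circumstances.

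**Available data.** Protocol 7.1 collects age and the "NIHSS score post onset before onset of thrombolysis" at screening. Eligibility allows NIHSS 5 to 25 and any age from 18. Randomization (protocol 3.4.1) is blocked 1:1 within centre; no stratification by severity or age is named.

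**The concern.** Stroke severity and age would be expected to predict a 90-day mRS of 0-1. The plan's own margin source is, by its title, about how treatment delay, age and stroke severity modify alteplase's effect. Both variables are in hand before allocation, so using them costs nothing in data collection. Leaving them out gives up precision in a trial whose margin allows only a 6.3% relative loss (1 - 0.937).

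The one patient-level covariate that is named cannot be programmed from the text. The pre-onset score can take only the values 0 and 1. The post-onset score has no eligibility limit and would partly reflect severity. These are different analyses.

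The protocol 12.4 sentence then makes adjustment depend on what the groups turn out to look like. It gives no candidate list, no threshold for a difference, and no role for the resulting estimate. The SAP plans between-group tests of baseline characteristics, which could serve as the selection step. In an open-label trial it is preferable that nobody has that choice to make.

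**Working it through.** **Inputs.** SAP section 6: control rate 59.32%, RR 1.07, margin 0.937, one-sided alpha 0.025, power 0.85, 642 per arm before dropout. Prognostic strength of NIHSS and age: not in the documents, so assumed and shown as a range.

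**1. Reproduce the planned size.**

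n per arm = (1.960 + 1.036)² × [(1-pT)/pT + (1-pC)/pC] / (ln RR - ln 0.937)²

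- pC = 0.5932; pT = 1.07 × 0.5932 = 0.6347
- Bracket: 0.5755 + 0.6858 = 1.2613
- Distance: 0.06766 + 0.06507 = 0.13273
- n = 8.978 × 1.2613 / 0.13273² = 642.8

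This agrees with the stated 642.

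**2. Power if adjustment removes a share R of the variance of log RR.**

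Unadjusted variance at n = 642 is 1.2613/642 = 0.0019646 (SE 0.04432).

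Power = Φ(0.13273 / √[0.0019646 × (1-R)] - 1.960)

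The equivalent extra patients are 1284/(1-R) - 1284, where 1284 = 2 × 642.

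| R (assumed) | Power at RR 1.07 | Equivalent extra patients |
|---|---|---|
| 0 | 0.850 | 0 |
| 3% | 0.860 | 40 |
| 5% | 0.867 | 68 |
| 10% | 0.884 | 143 |
| 15% | 0.901 | 227 |

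**3. Is the range plausible, and is error control affected?** Simulation with 642 per arm and one standard-normal baseline covariate, comparing the standardized RR from a logistic model with the crude RR (2000 runs for power, 4000 at the margin).

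| Covariate OR per SD (assumed) | Variance reduction | Power, crude | Power, prespecified adjustment |
|---|---|---|---|
| 0.70 | 3% | 0.865 | 0.872 |
| 0.50 | 9-10% | 0.864 | 0.896 |
| 0.35 | 18% | 0.845 | 0.910 |

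One-sided type I error at a true RR of 0.937:

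| Strategy | Type I error |
|---|---|
| Crude | 0.024-0.025 |
| Prespecified adjustment | 0.024-0.025 |
| Adjust only if the covariate differs at p<0.05 | 0.021-0.023 |
| Claim the better of crude and adjusted | 0.029-0.034 |

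Monte Carlo standard error near 0.025 is √(0.025 × 0.975/4000) = 0.0025. Only the last row suggests inflation.

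**4. Which document governs the open sentence?** Protocol 12.2 says the detailed analysis follows the SAP. SAP section 1 says it is to be read together with the protocol, and SAP section 9 refers back to the protocol for detail. Neither cancels the protocol 12.4 sentence, so it still applies.

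**The case against.** **The logistic model is not the deciding analysis.** This stands. Non-inferiority is judged on the RR, and the odds ratio has no margin. Changing covariates in that model alone would change no decision. The precision gain arises only if an adjusted RR is given a stated role.

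**Omitting covariates is not an error.** This also stands. A reader might infer that the primary RR is biased or its type I error inflated; the documents do not support that. With 1:1 randomization the crude analysis holds its level, and the planned 85% power is met on the plan's own assumptions.

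**A reader might conclude that the model adjusts for a near-constant score.** That is true only of the pre-onset mRS. With two scores recorded and neither named, the supportable statement is that the covariate is undefined.

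**A reader might see error inflation in the protocol 12.4 rule.** Adjusting only after an observed imbalance was, if anything, slightly conservative. Inflation needs a free pick of the better result, which no section permits, although none rules it out. The defect is an unplanned choice.

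**A reader might say that the secondary models exclude centre.** They are silent on it, and SAP section 9 asks in general terms for the centre effect to be handled. The method is missing.

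**Onset-to-treatment time looks like a natural third covariate.** It should not be used. Protocol 6.1 places dosing after randomization and the flow chart records thrombolysis time at the 0 h visit, so it is fixed once open-label allocation is known and could differ by arm.

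**Conclusion.** The point holds as an avoidable loss of precision and an incompletely specified adjustment. No efficacy analysis uses baseline NIHSS or age, the baseline mRS covariate is ambiguous, and a data-driven covariate rule remains in force.

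Under an assumed 3-15% variance reduction, power at RR 1.07 would rise from 85% to about 86-90%, worth about 40 to 227 patients. The strongest simulated covariate gave 18% and power 0.91, just outside that range. The gain rests wholly on prognostic strength that the documents do not give; the lower end is small. The absence of adjustment does not threaten the validity of the centre-stratified RR.

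**What to change.** Before database lock:

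1. Prespecify one model for the primary endpoint: treatment, centre, baseline NIHSS and age. If a time variable is wanted, use onset-to-randomization time.
2. Report the standardized marginal RR from that model with its 95% CI against 0.937, and keep the centre-stratified Mantel-Haenszel RR. State in advance which of the two decides non-inferiority; the other is reported alongside.
3. Say which screening mRS is the baseline score wherever that covariate is kept.
4. Name centre and the same covariates in the secondary logistic and ordinal models.
5. Delete the group-differences sentence from protocol 12.4, or state in the SAP that it no longer applies.

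The cost is a change of wording and a little programming, with no new data. Small centres will need a prespecified pooling rule or a random effect. If the sponsor prefers to leave NIHSS and age out, a short justification and items 3 to 5 would still close the ambiguity, without the precision gain.
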